Primary objective: To test the efficacy of NMBR with sugammadex, compared to neostigmine, to reduce inadequate NMBR and its related hypoventilation during the immediate postoperative period after kidney transplantation surgery, after adjusting for qTOF recovery and morphine equivalents received. We define hypoventilation as the incidence of ≥ 1 minute-long events of MV $<40\%$ of expMV. Minute ventilation will be measured continuously with a noninvasive respiratory volume monitor for the first 3h after the end of surgery or until meeting discharge criteria from the post-anesthesia care unit (PACU) (if sooner than 3h).

Secondary objective: To test the efficacy of NMBR with sugammadex, compared to neostigmine, to reduce inadequate NMBR and its related hypoventilation during the first 3 postoperative days in patients after kidney transplantation surgery, after adjusting for qTOF recovery and morphine equivalents received. We define hypoventilation as the incidence of ≥ 1 minute-long events of MV $<40\%$ of expMV. Minute ventilation will be measured continuously with a noninvasive respiratory volume monitor for up to 3d after surgery or until meeting end of monitoring criteria (if sooner than 3d)

Additional secondary objectives: To test if NMBR with sugammadex, compared to neostigmine, reduces patient's reported dyspnea scores (with the validated Patient-Reported Outcomes Measurement Information System, PROMIS®, assessment), decreases postoperative pulmonary complications (PPCs)

possibly related to inadequate NMBR after kidney transplantation surgery (i.e. respiratory insufficiency, gastric aspiration, pneumonia), improves kidney graft outcomes and reduces hospital resources utilization (i.e. hospital length of stay, ICU admission) and estimated healthcare costs.

II. Background and Significance/Preliminary Studies:

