
There is insufficient information on the use of sugammadex for NMBR in patients with kidney dysfunction. The clearance of sugammadex is proportional to creatinine clearance (ClCr), and thus delayed with kidney dysfunction[22-25]. However, no safety adverse events related to inadequate NMBR or delayed recurrence of NMB have been observed in patients with kidney dysfunction receiving sugammadex[26]. Nonetheless, patients with kidney impairment often receive the cholinesterase inhibitor neostigmine for NMBR. Neostigmine provides a slower and less effective NMBR than that achieved with sugammadex in the overall population, and its overdose is itself associated with increased muscle weakness[3, 10, 27-31] and postoperative pulmonary morbidity[1, 12]. It is critical to investigate the effect of sugammadex as NMBR in patients with kidney dysfunction.

Thus, we are proposing to randomize patients with severe kidney dysfunction (ClCr <30 mL/min) undergoing kidney transplantation surgery to receive either NMBR with sugammadex (intervention) or neostigmine (control) following qTOF monitoring-guided and FDA-approved doses. Despite their severe kidney disease these patients are receiving a kidney transplantation surgery. The exact kidney function during the first hours after reperfusion of the graft kidney in the receiving patient is unknown. Thus the clearance and duration of effect of sugammadex in kidney transplant recipients during the early postoperative period is unknown but relevant. Their kidney function is expected to improve over the following days to months after transplant, and considered stable 6-12 months after transplant.

III. Research Methods

A. Outcome Measure(s)

The **primary outcome** will be the frequency of patients with one or more ≥ 1 minute-long episodes of hypoventilation within 3 hours after the end of surgery or until meeting discharge criteria from the PACU (if sooner than 3h), assessed with a continuous noninvasive respiratory volume monitor that will be blinded to care providers.

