We have designed a prospective randomized double-blind single center study on 100 patients with severe kidney failure undergoing kidney transplantation surgery. Patients will be randomized to receive either NMB with rocuronium and sugammadex for NMBR (intervention group) or NMB with rocuronium and neostigmine for NMBR (control group). Respiratory function will be objectively monitored starting in PACU and during the first 3 postoperative days or until end of monitoring criteria are met. A blinded assessor will record the frequency of hypoventilation events as well as the accumulated minutes of hypoventilation. Quantitative TOF monitoring will be evaluated by a blinded investigator. Additional data related to patient's comorbidities, morphine equivalents (mg/kg) received, validated dyspnea patient-reported scores, pulmonary complications, kidney graft relevant data and outcomes, and hospital resource utilization and estimated costs will also be collected.

After signing informed consent, patients will be randomized to receive, during kidney transplant surgery, NMB with rocuronium and NMBR with either sugammadex (intervention group) or neostigmine (control group). Both groups will receive intraoperative NMB agents and reversal medications as guided by qTOF monitoring and following FDA-approved doses (see details below). In the PACU, we will perform continuous monitoring of their MV during their PACU stay and assess qTOF at selected time points in all patients. Institutional discharge criteria from PACU is based on an Aldrete's score[33] ≥ 8 assuming there are no discharge concerns by the patient's healthcare providers (PACU nurse, anesthesiologist and/or surgeon). After discharge from PACU and during the first 3 postoperative days (or until end of monitoring criteria if sooner) we will maintain the continuous MV monitoring and daily quantitative TOF assessment, collect opioids received and data relevant to pulmonary complications, kidney graft outcomes and estimated healthcare costs. At the postoperative surgery clinic visit or by phone interview we will collect patient's subjective dyspnea scores and compare to their baseline (with a validated questionnaire), as well as updated PPCs, kidney graft outcomes, hospital resources utilization and estimated healthcare costs.

Preoperative phase

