- NMBR brief protocol: The sugammadex (intervention) or neostigmine (control) will be administered at the end of the surgery. The goal will be to administer the appropriate NMBR medication when ≥ 2 twitches are objectivized with the qTOF monitor. NMBR drugs and dosing for each group will follow standard of care FDA-approved doses, as follows: Sugammadex 2 mg/kg will be administered when spontaneous recovery has reached the reappearance of the second twitch in response to TOF stimulation.

	Sugammadex dosing (mg/kg)	Neostigmine dosing (mg/kg)
T4 recovered	2	0.03-0.05 (max 5 mg)
T2/T3 recovered	2	0.05-0.07 (max 5 mg)
T0/T4 with 1-2 post-tetanic twitches present or T1 recovered	4 or wait	Wait

Overdosing of neostigmine will be avoided to prevent neostigmine-induced muscle weakness. Neostigmine will be administered simultaneously with the appropriate glycopyrrolate dose (0.2 mg per 1.0 mg of neostigmine).

Extubation will be performed following the usual standard of care criteria of adequate level of consciousness, presence of airway protection reflexes and spontaneous ventilation parameters in addition to quantitative TOF $T4/T1 >0.9$. The following times (minutes) will be recorded: NMBR administration-to-T4/T1 >0.9 , NMBR administration-to-extubation, total operating room time.

Postoperative in-hospital phase

The blinded investigator will collect the following study-related information:

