- Continuous respiratory volume monitoring: From the moment of arrival to the PACU, the patient will be continuously monitored with the FDA-approved noninvasive respiratory volume monitor ExSpiron® (Respiratory Motion, Inc.) available at UCH. This electrical impedance-based monitor uses a sensor that is applied to the chest's skin at three pre-determined locations: sternal notch, xiphoid and right mid-axillary line at the level of the xiphoid. By monitoring the thoracic impedance to a high frequency current it continuously assesses the estimated volume between three thoracic points of reference. It provides 5-second updates of average respiratory rate, tidal volume and MV volume (= respiratory rate * tidal volume). Calibration is no longer required, but it requires the user to enter some patient's information (gender, and height + weight, or body surface area) for the mathematical calculation of tidal volume and minute volume for that particular patient. By calculating the expected minute volume ($expMV =$ tidal volume times respiratory rate) based on patient's characteristics it provides the option to compare the observed estimated MV and detect hypoventilation events. The settings of hypoventilation events are customizable by duration and the percent of expected MV below which the MV is observed. This monitor will be blinded to healthcare providers to avoid biasing routine standard of care. Continuous data from this monitor (respiratory rate, tidal volume and MV volume) are automatically stored and will be exported at the end of PACU and daily for up to 3 days or sooner if the patient fulfills the following end of monitoring criteria: is discharged from the hospital; or is freely ambulating (defined as patient walking outside of the hospital room ≥ 2 times a day) and shows no signs or symptoms of respiratory complications, swallowing problems or muscle weakness. While attached to the monitor, this will be secured to a wheeled pole to facilitate the process for patient mobilization and ambulation. Once the respiratory volume data is exported, we will measure the incidence of hypoventilation as defined below (primary outcome) during PACU and daily for up to 3 postoperative days, as well as characterize the distribution of respiratory volume parameters (average, median, percentiles) during PACU and daily for up to 3 postoperative days.

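### The primary window is counted from the end of surgery, but minute ventilation is recorded only from PACU arrival, so the plan cannot measure the window it names

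*Combined protocol and SAP*

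**What the plan says.** **Where the clock starts.** The Clinical Hypotheses, the Primary objective, section III.A (Outcome Measures) and the hypothesis restated in III.C all count the primary window from the end of surgery. It closes at 3 hours, or when PACU discharge criteria are met if that is sooner. The Primary objective adds: "Minute ventilation will be measured continuously with a noninvasive respiratory volume monitor for the first 3h after the end of surgery".

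**Where the recording starts.** The design summary in III.C says: "Respiratory function will be objectively monitored starting in PACU". The continuous monitoring item under the postoperative in-hospital phase says: "From the moment of arrival to the PACU, the patient will be continuously monitored". No section starts the monitor in the operating room or at extubation.

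**How the outcome is scored.** Variables/Time Points of Interest (III.F) classifies each patient from the exported trace as having at least one event or none. It describes monitoring over the PACU stay and states no 3-hour cap. Statistical Methods and Power/Sample Size likewise speak of events or incidence in PACU.

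**What lies between the two starts.** The reversal protocol gives the study drug at the end of surgery. For the next step it says "Extubation will be performed following the usual standard of care criteria", with T4/T1 >0.9 required in addition. The Background says: "Neostigmine provides a slower and less effective NMBR than that achieved with sugammadex in the overall population". Times from reversal to T4/T1 >0.9 and to extubation are listed as additional outcomes.

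**The concern.** The estimand and the measurement do not share a time origin. Two consequences follow, and they differ in strength.

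1. **Certain from the text.** The minutes from the end of surgery to PACU arrival belong to the named window but are not recorded in either arm. They include the first breaths after extubation, and the Background itself places residual weakness at extubation as well as in PACU. No rule says how the unrecorded part is handled.

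2. **Conditional.** If the window closes 3 hours after surgery, a patient who reaches PACU later has fewer minutes in which to show a first event. The outcome is any event, and the primary logistic model has no term for monitored time. If neostigmine patients arrive later, some control events would not be seen and the odds ratio would move toward 1. Randomisation does not correct this, because the delay would follow from the assigned drug.

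At stake are which period the primary result describes and, to an unknown degree, whether both arms are observed for equal time within it.

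**Working it through.** **Step 1: reproduce the plan's figure.** Inputs from Power/Sample Size: 76% v 38%, alpha 0.05 (taken as two-sided), 40 per group less up to 6 dropouts = 34.

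Power = Φ{[|p1 − p2|√n − 1.96√(2p̄(1 − p̄))] / √(p1(1 − p1) + p2(1 − p2))}, with p̄ = 0.57.

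- Numerator: 0.38 × √34 − 1.96 × √0.4902 = 2.216 − 1.372 = 0.844.
- Denominator: √(0.1824 + 0.2356) = 0.647.
- Ratio 1.305, so power = 90.4%.

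Solving for 90% gives n = 33.5, rounded up to 34. The stated 34 and 90% reproduce, so the sample size calculation is not in question here.

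**Step 2: illustrate late entry under an end-of-surgery cap.** The documents give no minutes, so these are assumptions:

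- every patient is followed to the 180-minute cap;
- the event rate is constant, and true 180-minute incidence is 76% v 38%;
- sugammadex patients enter at time zero, and neostigmine patients d minutes later.

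Control rate h = −ln(0.24)/180 = 0.00793 per minute. Observed control incidence = 1 − exp(−h(180 − d)). For d = 30: 1 − exp(−0.00793 × 150) = 1 − 0.304 = 69.6%.

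| Extra delay d (min) | Control minutes lost | Observed control incidence | Odds ratio | Power, 34 per arm | Power, 40 per arm |
|---|---|---|---|---|---|
| 0 | 0% | 76.0% | 0.194 | 90.4% | 94.5% |
| 5 | 2.8% | 75.0% | 0.204 | 88.6% | 93.2% |
| 10 | 5.6% | 74.0% | 0.215 | 86.6% | 91.6% |
| 20 | 11.1% | 71.9% | 0.240 | 81.6% | 87.6% |
| 30 | 16.7% | 69.6% | 0.268 | 75.3% | 82.1% |

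**Step 3: relax the constant common rate.** Let risk vary between control patients (gamma frailty, variance 1, also an assumption) and keep 76% at 180 minutes. Then incidence = 1 − 1/(1 + H), with H = (1/0.24 − 1)(180 − d)/180. For d = 10, 20 and 30 this gives 74.9%, 73.8% and 72.5%, with power at 34 per arm of 88%, 86% and 83%. The losses are smaller.

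**Step 4: an equal gap in both arms.** If both arms enter 10, 20 or 30 minutes late under constant rates, incidence is 74.0% v 36.3%, 71.9% v 34.6% or 69.6% v 32.9%. Power at 34 per arm is 89.6%, 88.6% or 87.4%. A shared gap costs little power, but the named period is still not measured.

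**Step 5: when the cap matters.** Late arrival shortens observation only for patients still short of PACU discharge criteria 3 hours after surgery. If the window is the PACU stay, as III.F reads, late arrival costs no minutes. The documents do not give the share of patients who would reach the cap.

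**The case against.** The best defence is that the working definition is the one in the analysis sections: PACU arrival to discharge readiness, with no 3-hour cap. On that reading both arms are observed from the same operational start and late arrival removes nothing. Even with the cap, the delay that depends on the drug is mainly the wait for T4/T1 >0.9, when the patient is still intubated. Those are not spontaneous-breathing minutes in which control events go unseen. Extubation also requires consciousness, airway reflexes and spontaneous ventilation, which may dilute any difference between drugs. No section makes transfer time depend on arm.

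Much of this stands. A reader might infer that treatment-caused unequal exposure is a fact of this design, or that power will fall to 75%. The documents support neither. The first depends on which window applies and on how many patients reach the cap. The second is the worst cell of an illustration with assumed delays, all six dropouts in each arm and full follow-up to the cap. A reader might also infer that every event before PACU arrival turns a patient into a non-event. That is true only of a patient with no later event in PACU.

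The defence does not remove the contradiction. Four places name the end of surgery as origin, the Primary objective claims continuous measurement from it, and nothing reconciles that with a monitor started in PACU. The end of surgery is not defined as a time stamp either.

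**Conclusion.** The inconsistency is established from the text: the primary window starts at the end of surgery, the recording starts at PACU arrival, and the analysis sections drop the 3-hour cap. The plan as written cannot measure the window named in its primary objective, and the minutes between extubation and PACU arrival are unobserved in both arms.

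Bias toward no difference is plausible but conditional. It needs the cap to apply, patients to reach it, and neostigmine patients to arrive later. The last is inferred from the Background and the extubation criteria, with no minutes given. For an assumed extra 5 to 30 minutes under the conditions of Step 2, control incidence would fall by 1.0 to 6.4 percentage points and power at 34 per arm to between 88.6% and 75.3%, with smaller losses if risk varies between patients. These figures show sensitivity and are not predictions. The point should be corrected; it does not invalidate the design.

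**What to change.** - **One origin for all patients.** Define the primary window as PACU arrival to 3 hours after PACU arrival, or until PACU discharge criteria are met if sooner. Use the same wording in the Clinical Hypotheses, the Primary objective, III.A, the monitoring and qTOF items and restated hypothesis in III.C, and Variables/Time Points of Interest.
- **Objective.** State that the trial measures hypoventilation in PACU.
- **Data.** Record monitor start and stop times for every patient.
- **Analysis.** Add a sensitivity analysis that accounts for monitored minutes, for example a complementary log-log model with log monitored time as offset. Keep it as sensitivity only, because monitored time arises after randomisation.

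**Cost.** Mostly wording, two time stamps and one extra analysis. The planned sample size is unchanged. The minutes between extubation and PACU arrival stay unmeasured, and the objective becomes slightly narrower.

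**Option.** Recording could instead start at extubation, but only if this is done for every patient without exposing the blinded assessor to the reversal drug. The plan assigns the monitoring to the blinded investigator and the intraoperative protocol to the unblinded one, so this needs a staffing solution. The origin should not be chosen patient by patient, since that would put two windows in one endpoint and could differ by arm.
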